4.3.1 Inclusion criteria: Participants will be women with early stage breast cancer currently enrolled in the Investigation of Serial studies to Predict Your Therapeutic Response with Imaging and Molecular AnaLysis (I-SPY TRIAL 2) or metastatic breast cancer enrolled in any clinical trial at the UAB Medical Oncology Clinic.

- 4.3.2 Exclusion criteria: Reasons for study exclusion include non-English speakers.
- 4.3.3 Sampling: Using standard-of-care patient-reported data collected in clinic, eligible patients will have screened positive for financial toxicity using the validated Comprehensive Score for financial Toxicity¹⁴ (COST; scored 0-44, scores < 26 indicate financial toxicity). Eligible patients will be approached during their clinic visit.
- 4.3.4 Informed consent: Informed consent will be obtained by a study coordinator through an informed consent form if the patient is interested.
- 4.4 Approach:
- 4.4.1 Aim 1: We will use the continual reassessment method phase I dose de-escalation clinical trial design under the assumption that financial toxicity may increase when the reimbursement “dose” decreases. Continual reassessment method is a model-based trial design that informs how the reimbursement “dosage” should be adapted for the next patient cohort based on past trial data.^{17, 18} The parameters to be used in the continual reassessment method are listed below.
- 4.4.1.1 Number of doses: We suspect six reimbursement dose amounts will be assessed. However, the number of dose amounts may decrease if a cohort finds their reimbursement dose amount as unsuitable (at least 1 of the 3 de-escalation criteria are not met in 2 patients), in which no dose de-escalation will occur in the next cohort.
- 4.4.1.2 Target toxicity level: The “toxicity” amount will be set at 40% (de-escalation criteria unmet in 2/5 patients) due to the low-risk nature of the “dose,” which is money rather than drug. Note that toxicity in this study is defined as suitability of the reimbursement dollar dose defined by 3 patient-reported measures: (1) financial toxicity (defined as out-of-pocket costs and accompanying psychological distress), (2) acceptability of the reimbursement dose, and (3) appropriateness of the reimbursement dose.
- 4.4.1.3 Dose-toxicity model: We will use a one-parameter logistic model.

Table 1. Dose toxicity skeleton.

[figure not shown]

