Dose number	Reimbursement dose amount	Decrease from starting dose in \$100 units	Prior probability of dose-limiting toxicity
1	\$1000	0.001	0.05
2	\$900	1	0.1
3	\$800	2	0.2
4	\$700	3	0.3
5	\$600	4	0.45
6	\$500	5	0.6

- 4.4.1.4 Dose-toxicity skeleton: Shown in **Table 1**.

As this is a dose de-escalation trial testing the feasibility of a dollar decrease in reimbursement from a maximum of \$1000, we are assessing the minimally tolerated dose. This refers to minimum dollar amount needed to alleviate trial-related financial toxicity for patients participating in I-SPY TRIAL2. With the data fitted to a logistic model, the minimally tolerated dose should be around

[figure not shown]
\$630 (i.e., a decrease of about \$370 from the starting dose of \$1000), and we would expect to detect it at the 5th dose (**Figure 1**).

Figure 1. Number and spacing of doses.

The operating characteristics also appear fine using a one-parameter logistic model (**Figure 2**).

Figure 2. Dose-toxicity scenarios.

4.4.1.5 Method of inference: We will use a Bayesian approach with informative priors.

4.4.1.6 Decision rules: We will choose the reimbursement dose with an estimated probability of a minimally acceptable, appropriate, and financial toxicity-limiting reimbursement dose closest to, but not greater than, the optimal reimbursement level.

4.4.1.7 Sample size and cohort size: Our total sample size for women with early stage breast cancer patients is 30, comprised of 6 cohorts of 5 patients

each. Our total sample size for women with metastatic breast cancer patients is also 30, comprised of 6 cohorts of 5 patients each.

4.4.1.8 Safety modifications: We expect minimal safety concerns with this study, since there is no medical/drug intervention.

4.4.1.9 Stopping rules: Early termination of phase I trials often occurs if adding additional patients to the trial will not result in changes to the identified optimal dose. As this is not a true phase I trial, but rather a health services pilot feasibility trial anchored within a phase I trial methodological design, no stopping will occur. Enrollment of our targeted 30 patients is necessary to understand our primary feasibility outcomes move our science forward to test outcomes in a larger randomized controlled trial.

[figure not shown]

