4.4.1.10 Patients will be dosed in cohorts of 5, with a maximum available sample size of 30 early stage and 30 metastatic breast cancer patients. The first cohort of 5 patients will be enrolled at the first reimbursement dose level of \$1000 per month for 4 months (\$4000 per patient in total). Patients will be surveyed biweekly to determine patient financial toxicity (COST tool¹⁹), acceptability of the reimbursement dose (Acceptability of Intervention Measure²⁰), and appropriateness of the reimbursement dose (Intervention Appropriateness Measure²⁰). Participants will be surveyed in-person at baseline, then biweekly over the phone. Semi-structured interviews will be completed in-person, with an option for completion virtually if the participant prefers. At the end of the 4-month period, reimbursement dose suitability will be determined as suitable by a cumulative negative financial toxicity screen and reimbursement dose deemed acceptable and appropriate in at least 4 patients (**Table 2**). If the reimbursement dose is found suitable (all of the 3 criteria are met in at least 4 patients), we will de-escalate the reimbursement dose for the next cohort of 5 patients (**Figure 3**). If the reimbursement dose is found unsuitable (at least 1 of the 3 criteria are not met in 2 patients), the next cohort of 5 patients will be enrolled at the same reimbursement amount (\$1000 per

Table 2. Reimbursement dose suitability and de-escalation criteria.

Reimbursement Dose Suitability Criteria	Instrument	Scoring	De-Escalation Criteria
Negative financial toxicity screen	Comprehensive Score for financial Toxicity (COST) ¹⁹	Scored 0-44, scores < 26 indicate financial toxicity	Average score ≥ 26
Reimbursement dose acceptable	Acceptability of Intervention Measure (AIM) ²⁰	4-item, 5-point Likert scale; higher scores indicate greater acceptability	Average score ≥ 4
Reimbursement dose appropriate	Intervention Appropriateness Measure (IAM) ²⁰	4-item, 5-point Likert scale; higher scores indicate greater appropriateness	Average score ≥ 4

month for 4 months). This sequence will continue until 30 patients have received the reimbursement intervention.

Figure 3. Study schema.

4.4.1.11 Justification of starting dose: The initial \$1,000 dose is based on a prior estimate of a logit model with $\beta_0 = -2.79$ and a slope $\beta_1 = 0.64$ for the dose in \$100 units. This was based on consensus among the investigators in the study and data from three studies:

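### The 40% target is described by the same result, 2 of 5 patients unmet, that the plan labels unsuitable, so the Aim 1 recommendation and the suitability verdict on the same amount can contradict each other

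*Combined protocol and SAP*

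**What the plan says.** All references are to the combined protocol and SAP.

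- **Target (4.4.1.2).** The toxicity "amount will be set at 40% (de-escalation criteria unmet in 2/5 patients"). The same section defines toxicity as suitability of the amount, judged on three patient-reported measures: financial toxicity, acceptability and appropriateness.
- **Number of doses (4.4.1.1).** A cohort's amount is "unsuitable (at least 1 of the 3 de-escalation criteria are not met in 2 patients"); the following cohort then does not step down.
- **Cohort rule (4.4.1.10).** Each cohort has 5 patients. The condition for stepping down reads "If the reimbursement dose is found suitable (all of the 3 criteria are met in at least 4 patients"). The opposite case begins "If the reimbursement dose is found unsuitable (at least 1 of the 3 criteria are not met in 2 patients), the next cohort of 5" and leads to enrolment at an unchanged amount.
- **Expected result (4.4.1.4).** The minimally tolerated amount is described as the least money that relieves trial-related financial toxicity. It is put at around $630, "and we would expect to detect it at the 5th dose". In Table 1 the 5th dose is $600, with a prior unmet probability of 0.45.
- **Selection rule (4.4.1.6).** The chosen amount has an estimated probability as near as possible to an optimal reimbursement level without exceeding it. That level is not defined or tied to the 40%.
- **Unsuitable as a verdict (4.4.1.11, closing paragraph).** The plan allows that patients may find even $1,000 unsuitable, will explore why in interviews, notes that the budget permits no more, and says the suitability data will inform the next study.

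**The concern.** In a dose-finding design the target is the failure rate that the recommended level is allowed to have. Here failure means that at least one suitability criterion is unmet, so the target and the suitability label describe the same outcome. The plan illustrates its target with 2 of 5 unmet, then calls 2 of 5 unmet unsuitable.

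If that word only meant that the next cohort does not step down, nothing would be wrong. But 4.4.1.11 uses it as a finding about whether the money is enough, and 4.4.1.4 describes the amount sought as one that relieves financial toxicity. Aim 1 is to identify a recommended amount. The final report could recommend an amount because it is on target and also record that cohorts given it found it unsuitable. Nothing in the plan says which statement prevails, so the choice would be made after the data are seen.

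**Working it through.** **Inputs.** Target 0.40 (4.4.1.2); cohort size 5 and the suitable/unsuitable rule (4.4.1.10); prior logit model with intercept -2.79 and slope 0.64 per $100 decrease from $1,000 (4.4.1.11); prior unmet probabilities (Table 1). I read unmet in 2 patients as 2 or more, the complement of at least 4 met.

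**Step 1: reproduce the plan's figure.** Solve -2.79 + 0.64x = logit(0.40).

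logit(0.40) = ln(0.4/0.6) = -0.405

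x = (-0.405 + 2.79)/0.64 = 3.73

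$1,000 - $100 × 3.73 = $627, which agrees with the stated $630. The 40% target is therefore what produces the expected amount.

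**Step 2: chance that a cohort at the target is labelled unsuitable.** With X, the number unmet, binomial(5, p):

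P(X ≥ 2) = 1 - (1-p)^5 - 5p(1-p)^4

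At p = 0.40: 1 - 0.0778 - 0.2592 = 0.663. The chance of being labelled suitable is 0.337.

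At exactly $630 (x = 3.7) the model gives p = 0.396 and P(X ≥ 2) = 0.656.

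**Step 3: the same chance at the tested levels around the target.**

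| Level | Table 1 p | P(unsuitable) | p from coefficients | P(unsuitable) |
|---|---|---|---|---|
| 4th, $700 | 0.30 | 0.472 | 0.295 | 0.462 |
| 5th, $600 | 0.45 | 0.744 | 0.443 | 0.733 |

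For the 5th level from the coefficients: -2.79 + 0.64 × 4 = -0.23, so p = 1/(1 + e^0.23) = 0.443.

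**Step 4: the selection rule against the 5th-dose expectation.** The 5th level is nearest to the target in absolute distance: |0.45 - 0.40| = 0.05, against |0.30 - 0.40| = 0.10 for the 4th. But 0.45 (or 0.443) exceeds 0.40. If the optimal level in 4.4.1.6 means the 40% target, its bar on exceeding that level excludes the 5th dose under the prior and leaves the 4th. Sections 4.4.1.4 and 4.4.1.6 then disagree about the expected answer.

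**Step 5: where the cohort rule is evenly balanced.** P(X ≥ 2) = 0.5 at p = 0.314. Under the same model, x = (ln(0.314/0.686) + 2.79)/0.64 = 3.14, or about $686. This describes how the rule behaves. The plan does not state it as a standard.

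**The case against.** The strongest reply is that a target rate and a cohort step rule do different jobs. A rule aimed at 40% should step down when failures are below 2 of 5 and stop stepping down when they reach it, which is what 4.4.1.10 does. The only design consequence of unsuitable is that the next cohort stays at the same amount. On this view the 66% is just the chance of staying put at the target. Section 4.4.1.6 selects by estimated probability, and no section requires the selected amount to have been labelled suitable.

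Most of that stands, and it rules out several stronger readings that a reader might infer:

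- *The plan would reject its own target amount.* It would not. An unsuitable finding holds the amount; it does not raise or discard it.
- *At least 4 of 5 met amounts to a second, 20% standard.* The documents state no such rate. The rule is evenly balanced near 31%, and a 20% target would fit it worse: at a 20% unmet rate P(0 or 1 of 5 unmet) = 1 - 0.263 = 0.737, so the rule would step below the target about 74% of the time.
- *The recommended amount would usually be labelled unsuitable, whichever level is chosen.* This depends on the level. If 4.4.1.6 leads to the 4th dose, the chance is about 47%.
- *The recommended amount is all the study produces.* Section 5.1.2 sets feasibility benchmarks and Aim 2 is qualitative.

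The reply does not dispose of the label itself. Section 4.4.1.2 defines toxicity as suitability, and 4.4.1.11 treats unsuitable as a conclusion about adequacy that will be carried into the next study. The word is therefore more than a step instruction, and the plan does not say how the conclusion relates to a 40% target.

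**Conclusion.** The point holds as a conflict between decision standards, not as a fault in the step rule. A result that is on target under 4.4.1.2 is inadequate under the label in 4.4.1.1 and 4.4.1.10. At the target rate a cohort of 5 would be labelled unsuitable 66% of the time, and about 74% at the 5th level, where the plan expects its answer (73% from the stated coefficients). Separately, the 5th-dose expectation does not fit 4.4.1.6 if the optimal level there is the 40% target.

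The probabilities assume independent patients with a common unmet rate and read 2 patients as 2 or more; exactly 2 of 5 at a 40% rate has probability 0.346. The dollar positions rest on the plan's prior model and may shift once data accrue. The check does not use the content of Figures 1 and 2. The wording conflict depends on none of these assumptions.

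**What to change.** Reconcile 4.4.1.1, 4.4.1.2, 4.4.1.6 and 4.4.1.10:

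1. State one standard that determines whether the recommended amount counts as adequate, and use it wherever the plan speaks of a suitable or unsuitable amount, including 4.4.1.11.
2. Word the cohort step rule separately, so that not stepping down is not in itself a verdict of inadequacy.
3. Define the optimal reimbursement level in 4.4.1.6 and say how it relates to the target.
4. Restate the $630 and 5th-dose expectation to match, and re-run Figures 1 and 2.

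The choice of standard is the sponsor's; no target rate or amount is proposed here. The cost is protocol wording and a re-run of the existing simulation, with no extra patients. The stated expected amount or level may change.

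### The selection rule in 4.4.1.6 is not limited to amounts a cohort actually received, so it can recommend an untried one; how often depends on a free parameter and prior that the text does not state

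*Combined protocol and SAP*

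**What the plan says.** - **Selection (4.4.1.6).** "We will choose the reimbursement dose with an estimated probability of a minimally acceptable, appropriate, and financial toxicity-limiting reimbursement dose". The rule takes the nearest estimate that does not exceed a set level. The level is not defined there; I read it as the 40% target of 4.4.1.2.
- **Model (4.4.1.3, 4.4.1.5, 4.4.1.11, Table 1).** "We will use a one-parameter logistic model", and "We will use a Bayesian approach with informative priors". The prior logit has intercept -2.79 and slope 0.64 per $100 decrease. Table 1 codes the decrease as 0.001 at $1000, then 1 to 5. Which parameter is free, and the form and variance of the prior, are not in the text. Figures 1-3 are not shown and may say more.
- **Movement (4.4.1.1, 4.4.1.10).** If 2 of 5 women fail at least one criterion, "the next cohort of 5 patients will be enrolled at the same reimbursement amount". Section 4.4.1.1 adds that "the number of dose amounts may decrease if a cohort finds their reimbursement dose amount as unsuitable". That limits what is tested, not what may be selected.
- **No stopping (4.4.1.9).** All six cohorts of 5 are enrolled, even if each is held at $1000.
- **Unsuitable starting amount (4.4.1.11).** The plan accepts that $1000 may fail and sends the reasons to the interviews. It does not say what is then recommended.

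**The concern.** There are six cohorts and six amounts, so a single hold before the last cohort leaves at least $500 untried. The model still gives $500 an estimated probability, and 4.4.1.6 can select it. For an untried amount the recommendation rests on the assumed curve and the prior, not on outcomes at that amount.

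Identifying the recommended amount is the stated purpose of Aim 1, and 4.4.1.11 says the suitability data inform the next study. In the worst case the trial would recommend a lower amount after the lowest amount actually paid had been found unsuitable.

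**Working it through.** **1. The plan's own figure.** Setting logit p = -2.79 + 0.64d equal to logit(0.40) = -0.405 gives d = (-0.405 + 2.79)/0.64 = 3.726, or $627. This matches the stated figure of about $630. Regressing the Table 1 skeleton on the coded decrease gives -2.793 and 0.647, so this coding appears to be the one the planners used. The prior probabilities from $1000 down to $500 are 0.058, 0.104, 0.181, 0.295, 0.443 and 0.601. Before any data the rule therefore picks the fourth amount, $700. The plan expects the fifth, whose 0.443 exceeds 0.40; those two statements need reconciling.

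**2. What outcomes at $1000 can teach the model.** With the intercept fixed, p at $1000 is expit(-2.79 + 0.001 × slope). To reach 0.40 the slope must be 3.726/0.001 = 3,726 times its prior value, a log-slope shift of ln(3,726) = 8.22. For a normal prior on the log slope:
- The log-prior penalty for that shift is 8.22²/(2 × SD²): about 135 at SD 0.5, 34 at SD 1.0 and 19 at SD 1.34.
- The most that 30 failures of 30 can add to the log-likelihood is 30 × ln(1/0.058), about 85.

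At SD 0.5 the prior always wins. At SD 1.0 and 1.34 enough failures overturn it.

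**3. All 30 held at $1000** (fixed intercept, posterior-mean probability, 40% ceiling, log slope integrated over ±12):

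| Prior SD | 10/30 fail | 15/30 | 24/30 | 30/30 |
|---|---|---|---|---|
| 0.5 | $700 | $700 | $700 | $700 |
| 1.0 | $800 | $800 | none | none |
| 1.34 | $800 | $1000 | none | none |

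At SD 0.5 the estimate at $1000 stays at 0.058 throughout. Five holds need at least 5 × 2 = 10 failures, so fewer than 10 of 30 cannot occur here. An integration range of only ±3 to ±6 misses the shift of 8.22 and falsely shows no change at the wider priors.

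**4. Chance that all cohorts stay at $1000.** If 80% of women are unsuitable there, one hold has probability 1 - (0.2⁵ + 5 × 0.8 × 0.2⁴) = 0.9933, and five holds 0.9933⁵ = 0.967. At 60% it is 0.634; at 40%, 0.128.

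**5. Simulated trials.** I applied the 4.4.1.10 rule to one group of 30 (six cohorts of 5), then the 4.4.1.6 selection. The figures are the share of trials selecting an amount below any given. The prior SDs and the scenarios other than Table 1 are assumptions.

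| True unsuitability | Fixed intercept, SD 0.5 / 1.0 / 1.34 | Back-solved labels, power model or free intercept |
|---|---|---|
| Table 1 | about 7-21% across the range | about 2-4% |
| 48% at $1000 rising in equal steps to 85% at $500 | 34% / 28% / 3% | 0-7% |
| 80% at every amount | 97% / 2% / 0% | 0% |

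In the fixed-intercept Table 1 case, essentially every untried amount selected is truly above 40% unsuitable. In the 80% case with SD 1.0 or 1.34, the rule finds no admissible amount in 92-97% of trials.

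**The case against.** The strongest reply is that the large figures come from one reading of the model. The plan does not say the slope is the free parameter, and 4.4.1.11 offers the coefficients to justify the starting amount. With labels back-solved from the skeleton, a power model or a free intercept, outcomes at $1000 do move the answer. At prior SD 0.5, 10/30 failures gives $1000 or $900, and 30/30 leaves no admissible amount in all three. This stands, and it limits the size of the point. It does not remove it: untried amounts were still selected under every form tried. With a tight prior (SD 0.25), the free-intercept form still names $900 after 30/30 failures at $1000.

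A second reply is that this is a pilot with its own feasibility benchmarks (5.1.2), and that investigators would see the failures and the interview data before planning the next study. That tempers the consequence. It does not supply a rule for the recommendation.

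A reader might infer that when every cohort is held the answer always comes from the prior, or that under no effect an untried amount is named about 97% of the time. The documents do not support either as a general statement. Both hold at SD 0.5 with a fixed intercept, and both fail at SD 1.0 and 1.34 and under the other forms. Nor is the problem of similar size whichever parameter is free.

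**Conclusion.** The point holds in a limited form. Section 4.4.1.6 has no eligible set, and 4.4.1.1, 4.4.1.9, 4.4.1.10 and 4.4.1.11 do not supply one. On the coding the plan appears to use, with a fixed intercept, the rule goes below any amount given in about 7-21% of trials even when Table 1 is right. With an informative prior (SD 0.5) it would name $700 after 30 failures of 30 at $1000. Under the other one-parameter forms the problem is uncommon: about 2-4% with Table 1 true.

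This rests on reading the undefined level as 40%, on the 4.4.1.10 rule governing movement, and on assumed prior SDs. Because the stated rule can return a wrong recommendation, this is more than missing detail and should be amended.

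**What to change.** Amend 4.4.1.6 so that:
- **(a)** the recommended amount is chosen only among amounts received by at least one full cohort, and any lower amount the model favours is reported as a hypothesis for the next study;
- **(b)** the trial reports that no tested amount is recommended when the observed data at the tested amounts exceed the plan's own 40% level.

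Part (b) is needed because (a) alone would recommend $1000 after 30/30 failures under the fixed-intercept, SD 0.5 model, where the estimate stays at 0.058.

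In 4.4.1.3 and 4.4.1.5, state the free parameter and the prior's form and variance. Replace the 0.001 code, for example with labels back-solved from the skeleton, so that outcomes at $1000 inform the fit.

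The cost is a few sentences and a refit of the planned model, with no added patients or data. The downside is real if suitability is good everywhere: the recommendation may be $100 or more above the model's extrapolation. At 15% unsuitable throughout, this affects about 35-45% of trials under the fixed-intercept model and about 1-6% under the others.

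### Section 4.4.1 states a model-based CRM, but Section 4.4.1.10 assigns each cohort by a count on the latest five patients, and the visible text does not say which governs

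*Combined protocol and SAP*

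**What the plan says.** Section 4.4.1 says a CRM will be used and describes it as a model-based design that informs how the amount "should be adapted for the next patient cohort based on past trial data". The subsections that follow are introduced as its parameters: a 40% target (4.4.1.2), a one-parameter logistic model (4.4.1.3), the Table 1 skeleton (4.4.1.4), Bayesian inference with informative priors (4.4.1.5), and a rule choosing the level whose estimated probability is "closest to, but not greater than, the optimal reimbursement level" (4.4.1.6). Section 4.4.1.6 does not say whether it applies to every cohort or only to the final choice.

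Section 4.4.1.10 gives the operating instruction. If all three criteria are met in at least 4 of 5 patients, "we will de-escalate the reimbursement dose for the next cohort of 5 patients". If 2 patients fail at least one criterion, "the next cohort of 5 patients will be enrolled at the same reimbursement amount", with the $1000 payment given in brackets. Then: "This sequence will continue until 30 patients have received the reimbursement intervention". Section 4.4.1.1 repeats only that after an unsuitable cohort the number of amounts may fall, "in which no dose de-escalation will occur in the next cohort".

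On performance, Section 4.4.1.4 puts the target amount near $630, adds that "we would expect to detect it at the 5th dose", and states: "The operating characteristics also appear fine using a one-parameter logistic model". The analysis list in 5.1.3 contains no model fit.

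**The concern.** A CRM pools all cohorts, re-estimates the dose-response curve and can move in either direction. The rule in 4.4.1.10 looks only at the cohort just finished and can only step down or hold. If all five patients on a lower amount found it unsuitable, the next five would receive that same amount.

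Two things are at stake. Staff following 4.4.1.10 and a statistician following 4.4.1 could each comply with the protocol and give the next cohort different payments. And if Figure 2 was produced for a CRM, its assurance would not carry over to the trial as run. The participants have already screened positive for financial toxicity. The protocol itself allows for more unsuitability than the 5% that Table 1 puts at $1000: 4.4.1.11 says $1000 may be found unsuitable, and Section 8 says the maximum may fall short of break-even.

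**Working it through.** **1. The plan's own figure.** Inputs: intercept −2.79 and slope 0.64 per $100 (4.4.1.11), target 40% (4.4.1.2). Solve logit(0.40) = −2.79 + 0.64x, so x = (−0.405 + 2.79)/0.64 = 3.73. The amount is $1000 − $373 = $627, which agrees with the stated $630.

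**2. Count rule, exact.** Read 2 patients as 2 or more. With true unsuitability p, P(step down) = (1−p)^5 + 5p(1−p)^4.

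| Amount | p (Table 1) | P(step down) | Expected patients of 30 |
|---|---|---|---|
| $1000 | 0.05 | 0.977 | 5.12 |
| $900 | 0.10 | 0.919 | 5.44 |
| $800 | 0.20 | 0.737 | 6.74 |
| $700 | 0.30 | 0.528 | 7.74 |
| $600 | 0.45 | 0.256 | 4.51 |
| $500 | 0.60 | (lowest level) | 0.45 |

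The last column walks six cohorts of 5 through these probabilities. Patients above 40%: 4.51 + 0.45 = 4.96. The sixth cohort is at $800, $700, $600 or $500 with probability 0.03, 0.33, 0.55 and 0.09.

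**3. Paths on which a CRM and the count part.** The prior variance and the fixed logistic parameter are not stated, so these rest on assumptions.
- Unsuitable 0/5 at $1000, 1/5 at $900, 5/5 at $800. The count holds at $800. With the intercept fixed at −2.79 and prior SD 1.158, the posterior estimates are 6%, 39% and 82%, and the model returns to $900. Most assumed models do the same. A tight prior (power model, SD 0.5) puts $800 almost exactly at 40% and could hold.
- Unsuitable 0/5, 0/5, 0/5, then 2/5 at $700. The count holds at $700. In the same model $600 is estimated at 32%, so a CRM without further restriction steps down.

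**4. Size, using the rule proposed under the fix.** Start at $1000, at most one step down, return allowed, no step down after 2 or more of 5 unsuitable. All outcome paths were enumerated under six assumed models: power model with prior SD 0.5, 1.0 and 1.5; logistic with intercept 3; intercept −2.79 fixed; slope 0.64 fixed (prior SD 1 for the last three). Ceiling means the lowest amount with posterior mean at or below 40%; closest means the posterior mean nearest 40%.

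Expected patients above 40%, per population of 30:

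| Assumed truth | Count | Proposed, ceiling | Proposed, closest |
|---|---|---|---|
| Table 1 | 5.0 | 2.5–4.0 | 4.3–4.6 |
| One level worse (10, 20, 30, 45, 60, 75%) | 9.2 | 5.4–7.1 | 7.5–8.6 |
| Two levels worse (20, 30, 45, 60, 75, 85%) | 14.1 | 7.3–11.1 | 10.9–13.6 |

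**5. What does not improve.**
- Correct final selection, proposed minus count, over these three truths and both readings: −2.3 to +1.3 percentage points in five models, and 1 to 14 points lower with the written intercept fixed.
- One level milder (2, 5, 10, 20, 30, 45%; assumed), ceiling reading: about 1 to 4 points lower in all six models. Two levels milder (1, 2, 5, 10, 20, 30%; assumed): 0 to 5 points lower.
- On the closest reading with Table 1 true, $600 is the correct level. Patients treated there fall from 4.5 to between 4.0 and 4.2.
- Without the 4-of-5 bar, a CRM on the closest reading puts 6.1 to 6.4 patients above 40% with Table 1 true, against 5.0 under the count. The bar should therefore stay.

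**The case against.** The strongest defence is that the sentence in 4.4.1 only explains what a CRM is. Section 4.4.1.10 is the one place that tells staff what to pay, 4.4.1.2 ties the 40% target to 2 of 5 patients, and 4.4.1.6 fits a final choice. On that reading the count assigns and the model selects at the end. This is workable, but the protocol does not say it, 4.4.1 speaks of the next cohort, and 5.1.3 lists no model fit at any stage. Nor can the count be just a limit on the CRM, because such a limit would still let the model move back up.

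Other parts of the defence stand. The hold sentence is written for the $1000 cohort; holding at lower amounts is inferred from the statement that the sequence continues. The no-step-down wording in 4.4.1.1 is compatible with a CRM. Figures 2 and 3 are not available, so a return step may be drawn there. The feasibility benchmarks in 5.1.2 do not depend on the assignment rule. The cost data in 4.4.1.11 also allow for milder unsuitability than Table 1, where the model-based rule selects slightly worse.

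A reader might go further in three ways that the documents do not support:
- That Figure 2 simulated the wrong rule. Which rule it simulated cannot be checked.
- That the two instructions disagree in 38–50% (ceiling) or 11–18% (closest) of trials. Those rates compare the count with the rule proposed here, not with a CRM stated in the protocol.
- That ending at $600 is an overshoot. Section 4.4.1.4 expects the fifth dose.

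**Conclusion.** The inconsistency is real and the visible text does not resolve it: the stated design adapts by model, while the written assignment rule does not. This conclusion is textual and depends on none of the simulated figures.

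The main gain from correcting it is that the trial run would match the design named. The further gain, fewer patients on amounts above 40%, is modest if Table 1 is true and larger if unsuitability is higher. It rests on assumed priors and parameterisations, on assumed shifts of Table 1, and on the inferred hold below $1000. There is no case that the count rule leads to a worse final recommendation. Confidence is high on the text and the exact count-rule figures, and moderate on the model-based ranges. Severity is minor to moderate; the wording should be fixed.

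**What to change.** Amend 4.4.1.10 so that each next cohort receives the level chosen under 4.4.1.6 from the posterior on all data to date in that population, at most one step down, with return up to $1000 allowed. Keep the 4-of-5 count only as a bar to stepping down. State the fixed logistic parameter, the prior variance, and whether 40% is a ceiling. Choose the parameterisation by simulation first, including milder truths than Table 1, because fixing the written intercept can lower correct selection. Confirm that Figure 2 simulated this rule, or rerun it.

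If the count rule is intended, drop the statement that the model adapts the next cohort, say that the model is used only for the final choice, and give operating characteristics for the count rule.

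Cost: protocol wording, one simulation check, and up to five interim fits per population by the biostatistician already budgeted in 5.1.1, on data the count already needs. No extra patients or follow-up. Expected payments under the count with Table 1 true are 4 × (5.12×$1000 + 5.44×$900 + 6.74×$800 + 7.74×$700 + 4.51×$600 + 0.45×$500) = $95.0k per population; under the proposed rule they are $95.3k to $96.5k. With the two-level worse shift they rise from $103.5k to between $104.2k and $108.7k. All stay below 30 × $4000 = $120k, the no-de-escalation case that 5.1.1 used to set cohort size. The price of the model-based option is the possible small loss in final selection shown above.
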